Patients will be followed for survival after the end of treatment (EoT) visit every 3 months for 12 months, or until withdrawal of consent, death, or the end of study (i.e., when the last patient in the study has been followed up on study treatment for at least 1 year, or completed at least 6 months of survival follow-up period after their last dose of study treatment, has withdrawn consent, has died, or has been lost to follow-up), whichever occurs first. End of treatment imaging will be performed ≤ 28 days after treatment discontinuation for patients who discontinue for reasons other than PD if their previous scan was performed >3 weeks before EoT.

After discontinuation of study treatment, patients will also be followed for safety 30 days after EoT and then every 3 months for 12 months and for PFS approximately every 3 months after EoT visit until PD, death or initiation of the subsequent anti-melanoma treatment (if a patient discontinues from the treatment due to reasons other than PD).

Statistical Methods:

CCI

Analysis Populations:

The modified intent-to-treat (mITT) population will consist of all patients who receive at least one dose of any study treatment.

The safety population will include all enrolled patients who receive at least 1 dose of both study drugs.

Efficacy Analyses:

The primary efficacy endpoint of ORR (proportion of patients who achieve CR or PR) will be analyzed for each arm separately on the modified intent-to-treat (mITT) population which consists of all enrolled patients who received any study treatment. Estimated ORR with 95% confidence interval (CI) will be summarized for each arm.

Analyses of other efficacy endpoints will be specified in Section 12 of the protocol and the Statistical Analysis Plan (SAP)

Safety Analysis:

Continual monitoring of safety data will be performed by the independent Data Safety Monitoring Board (DSMB). Adverse events and concomitant medications will be coded according to medical dictionary for regulatory activities (MedDRA) and WHO Drug, respectively. Safety analyses will be performed on the Safety Population and will be presented by actual treatment arm.

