3.2. Schedule of Assessments

Table 1: Schedule of Assessments for Study XPORT-MEL-033 (42-Day Cycle)

Activity/Assessment	Screening ^a D -28 to -1	Cycles* 1			Cycles* ≥ 2			EoT Visit ≤ 28 Days Post-Treatment Discontinuation	Follow-up Visit ^b	
		D1	D3±2D	D15/D29 ±3D	D1	D3±2D	D15/D29 ±3D		30 days after EoTVisit +7D	Every 3 months until 12 months ±14D
Procedures										
Informed Consent	X									
Inclusion/Exclusion	X									
Demographics	X									
Medical history	X									
Concomitant Medications Review	X	Continuous					X	X	X	
Prior Melanoma Therapy	X									
Eligibility confirmation by Sponsor ^c	X									
ECOG Daily Living Performance Score	X	X		X						
Nutritional Counselling	X	Throughout, as needed								
Vital signs including weight	X	X		X			X			
Physical Exam – full	X						X		X	
Physical Exam – symptom directed		X		X				X		
Adverse Events ^d		Continuous								
Telephone contact ^e			X					X	X	
Collection of information regarding antineoplastic therapy after EoT								X	X	
Laboratory										
Hematology and Serum Chemistry	X	X		X	X		X	X		

Activity/Assessment	Screening ^a	Cycles* 1			Cycles* ≥2			EoT Visit	Follow-up Visit ^b	
		D -28 to -1	D1	D3±2D	D15/D29 ±3D	D1	D3±2D	D15/D29 ±3D	≤28 Days Post-Treatment Discontinuation	30 days after EoTVisit +7D
LDH	X	X			X			X		
Pregnancy test ^f	X	X						X	X	
CCI										
Drug Administration										
Selinexor		Selinexor will be administered once weekly (Days 1, 8, 15, 22, 29, 36 of 42-day cycle)								
Pembrolizumab		Pembrolizumab will be administered on Day 1 once every 6 weeks								
Anti-tumor Activity										
Tumor assessment by CT or MRI Scan	X	Tumor assessment will be performed every 9 weeks for 6 months, then every 3 months thereafter						X		

CT = computed tomography; D = day; ECOG = Eastern Cooperative Oncology Group; EoT = end of treatment; FU = follow-up; hCG = human chorionic gonadotropin; LDH = lactate dehydrogenase; MRI = magnetic resonance imaging; PDn = pharmacodynamics

* Cycles are 6 weeks in length.

^a Procedures that are performed as part of standard of care should not be repeated if they are within the screening window and are done prior to signing the ICF.

^b After discontinuation of study treatment for reasons other than PD, disease assessments should continue to be performed every 3 months until progression, start of new therapy or withdrawal of consent.

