6.2. End of Treatment

The end of treatment (EoT) visit will occur \leq 28 days post-treatment discontinuation. After discontinuation of study treatment, patients will be followed for PFS approximately every 3 months after EoT visit until PD, death or initiation of the subsequent anti-melanoma treatment (if a patient discontinues from the treatment due to reasons other than PD), and for survival every 3 months after end of treatment visit for 12 months or until withdrawal of consent, death, or the end of study (i.e., when the last patient in the study has been followed up on study treatment for at least 1 year or

completed at least 6 months of survival follow-up period after their last dose of study treatment, has withdrawn consent, has died, or has been lost to follow-up) whichever occurs first.

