10.3. Efficacy Assessments

10.3.1. Response criteria

Computed Tomography (CT) or Magnetic Resonance Imaging (MRI)

Disease response is based on tumor measurement using CT scans or, MRI. Scans will be performed at Screening (Day -28 to Day -1) and every 9 weeks for 6 months, then every 3 months thereafter until confirmed PD, death or consent withdrawal occurs. Scans at the EoT visit should be performed for patients who discontinue for reasons other than documented PD, if previous imaging was more than 6 weeks old. The same scan modality should be used for all assessments.

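### The protocol gives two scan schedules for patients who stop treatment without PD, and the SAP does not settle whether PD found on the later scans counts, so PFS and DOR can depend on why treatment ended

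*Protocol*

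**What the plan says.** **On treatment.** The Schedule of Assessments reads "Tumor assessment will be performed every 9 weeks for 6 months, then every 3 months thereafter". Section 10.3.1 gives the same intervals and runs them "every 9 weeks for 6 months, then every 3 months thereafter until confirmed PD, death or consent withdrawal occurs". Nothing in Section 10.3.1 changes the interval when treatment stops.

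**After stopping without PD.** Footnote b of the same schedule reads "After discontinuation of study treatment for reasons other than PD, disease assessments should continue to be performed every 3 months until progression". The synopsis follows these patients "for PFS approximately every 3 months after EoT visit until PD, death or initiation of the subsequent anti-melanoma treatment", and Section 6.2 says "patients will be followed for PFS approximately every 3 months after EoT visit until PD". Only the synopsis and Section 6.2 name the EoT visit as the starting point; footnote b names none. The EoT visit may take place up to 28 days after discontinuation, and the follow-up column carries a window ("Every 3 months until 12 months ±14D"). The end points differ too: footnote b, the synopsis and Section 6.2 stop at new therapy, while Section 10.3.1 does not list it.

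**EoT scan.** The synopsis says "End of treatment imaging will be performed ≤ 28 days after treatment discontinuation for patients who discontinue for reasons other than PD", with the condition "if their previous scan was performed >3 weeks before EoT". Section 10.3.1 requires the scan only when the previous imaging is more than 6 weeks old.

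**Analysis.** Protocol Section 12.4.1.2 defines PFS up to confirmed PD or death, and DOR up to PD or death, with no cut-off at treatment discontinuation. SAP Table 4-2, which covers both endpoints, counts documented PD as an event in row 3, provided two or more consecutive assessments were not missed. Row 5 lists treatment discontinuation plus 30 days among its censoring triggers and censors at the last adequate assessment before the trigger. The table does not say which row prevails. SAP Section 1.6 records no modification to the protocol's statistical section.

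**The concern.** A site can follow one part of the protocol to the letter and breach another. With up to 20 sites, patients in the same position could be scanned on different dates. PD is dated when it is seen, so the scan schedule is part of the definition of PFS and DOR. In the first 6 months the interval lengthens from 9 weeks to 3 months only for patients who stop without PD, for example for toxicity.

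The SAP then leaves open whether what those scans find is used. If it is, dating depends on treatment status. If it is not, patients who stop without PD leave the risk set about a month after stopping. That is harmless only if their later risk of progression matches that of patients who stay on treatment, which is doubtful when the reason is toxicity or clinical decline. The rule on missed consecutive assessments also needs a single calendar, because otherwise it is unclear which assessments were due.

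**Working it through.** The documents give no figure for scan timing, and the sample-size text is redacted, so there is nothing to reproduce. The checks below use the intervals stated above.

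**1. Interval length.** Mean detection lag is half the interval: 9/2 = 4.5 weeks against 13/2 = 6.5 weeks. The difference is 2 weeks, before allowing for the EoT scan and the new starting point. After 6 months both schedules are 3-monthly and differ only in phase.

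**2. One patient.** Last scan at week 9, treatment stopped at week 10, EoT visit at week 14 (10 + 28 days). The last scan is then 14 − 9 = 5 weeks old: the synopsis requires an EoT scan and Section 10.3.1 does not. Without it, the next scan is at 14 + 13 = week 27. Section 10.3.1 would have scanned at week 18, so the difference is 9 weeks. Under the synopsis trigger with EoT at week 12 (scan exactly 3 weeks old, so none required), the next scan is at week 25, a difference of 7 weeks.

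**3. Average shift if row 3 governs.** I simulated both schedules. Assumptions not in the documents:
- stopping uniform over weeks 2 to 26;
- exponential time to PD after stopping, with a median of 4.2 months, a figure the protocol quotes from another trial;
- EoT visit uniform over 0 to 28 days after stopping;
- EoT scan according to the trigger, then every 13 weeks from EoT.

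The comparison is the Section 10.3.1 calendar. Because 6 months is 26 weeks, the text does not settle whether a week-27 scan belongs to the 9-weekly phase, so both readings are shown.

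| Calendar | EoT trigger | Mean shift, all PDs | Share dated later | Mean shift, PDs before week 27 |
|---|---|---|---|---|
| Weeks 9, 18, 27, then 13-weekly | >3 weeks | +0.7 weeks | 53% | +2.9 weeks |
| Weeks 9, 18, 27, then 13-weekly | >6 weeks | +1.0 weeks | 55% | about +3.6 weeks |
| Weeks 9, 18, then 13-weekly | >3 weeks | +0.4 weeks | 54% | +0.75 weeks |
| Weeks 9, 18, then 13-weekly | >6 weeks | +0.65 weeks | 56% | +1.5 weeks |

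About 37% of the simulated PDs arise before week 27. On the week-27 calendar the other 63% are dated about 0.5 weeks earlier on average, which is why the overall shift is small.

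**4. What reaches the analysis if row 5 governs.** The earliest 3-monthly scan falls 13 weeks less the 14-day window after EoT, and EoT can be no earlier than the day of stopping: 91 − 14 = 77 days, always beyond 30. In the example the cut-off is 10 + 30/7 = week 14.3. The patient is censored at week 9, or at the EoT scan if one was done and showed no PD. PD seen at week 27 is not an event. A restored week-18 scan would also fall after the cut-off. In the simulation in step 3, 93% to 95% of the PDs arising after stopping are found after day 30.

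**The case against.** The best defence is that this is a wording conflict with little numerical effect. PFS and DOR are secondary, summarised as medians with confidence intervals by arm; both arms receive the same regimen and no PFS or DOR test is described. That stands, and it limits the importance of the point.

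A reader might infer more: that PD is dated later in patients who could not tolerate the regimen, so that poor tolerability lengthens PFS. The documents do not support this, for four reasons.
- On row 5, these PDs are not dated late; they are removed.
- On row 3, the shift is modest and goes both ways, because an EoT scan can catch PD before the next calendar scan would.
- With an assumed 6%, 12% or 18% stopping without PD in the first 6 months, and row 5 ignored, the simulated arm median stayed at 27.0 weeks or fell to between 25.9 and 26.5. In separate runs with an assumed 10% or 30% stopping and medians of 4.2 and 8.8 months, restricted mean PFS to 52 weeks rose by only 0.01 to 0.29 weeks.
- The 9-week example is close to the worst case. It needs the latest permitted EoT visit and the 6-week trigger.

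Nor is 4.2 months a benchmark in this plan. It appears only as background from another trial.

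It is also fair to object that changing the scans alone would not repair PFS if row 5 governs. That is right, so the SAP must change as well. None of this removes the contradiction: the protocol keeps scanning these patients expressly for PFS, and row 5 would discard what those scans find.

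**Conclusion.** The point holds as an inconsistency to be resolved in both documents. The protocol states two scan schedules and two EoT-scan triggers for patients who stop without PD, and SAP Table 4-2 can be read to count or to discard the PDs found afterwards.

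PFS and DOR can therefore depend on why treatment ended. If row 5 governs, the main route is potentially informative censoring; its size cannot be computed, because neither the share who stop without PD nor their later risk is given. If row 3 governs, the route is less frequent, re-anchored scanning. Under the stated assumptions PD is then dated 0.4 to 1.0 weeks later on average over all PDs, and 0.75 to 3.6 weeks later for PDs before week 27, depending on the trigger and on whether a week-27 scan is assumed. Individual dates move in both directions. No effect on the primary ORR endpoint was examined or is claimed.

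**What to change.** **Protocol.** Reconcile the synopsis, footnote b, Section 6.2 and Section 10.3.1 to one tumour-assessment calendar counted from first dose and independent of treatment status. State when the 3-monthly phase starts and whether scanning ends at new anti-melanoma therapy. Use one EoT-scan trigger throughout, and say that the EoT scan is additional and does not reset the calendar.

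**SAP Table 4-2.** Remove treatment discontinuation plus 30 days as a censoring trigger for PFS and DOR, so that PD found on these scans counts as the protocol defines. Report the version censored at discontinuation as a sensitivity analysis. Define missed assessments against the single calendar.

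**Cost.** Wording changes in both documents, one extra sensitivity analysis, and about one extra scan, at most two, per patient who stops without PD in the first 6 months. Section 10.3.1 already calls for those scans. Other patients are unaffected.

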4. INTRODUCTION

4.1. Melanoma

Melanoma is a malignant neoplasm of melanocytes derived from neural crest stem cells which produce melanin, and generally arises from UV exposure and genetic mutations (Byrne, 2017; Rebecca, 2020). While melanoma only accounts for about 1% of skin cancers, it is responsible for the majority of skin cancer mortality (Siegel, 2020). Over the past few decades, rates of melanoma have been rapidly increasing. In 2020, cases of newly diagnosed melanoma are estimated to be over 100,000, with 6,850 expected deaths (Siegel, 2020). Patients with stage IV melanoma have a median survival of 8 to 18 months after diagnosis, with metastasis to the brain as the most common complication (Balch, 2009; Rebecca, 2020).

Standard first line of treatment for patients with localized melanoma is surgical excision and complete lymphadenectomy for patients with involved regional nodes (Davis, 2019; Garbe, 2011). Until 2011, standard treatment for metastatic melanoma included, radiation therapy, surgery, and/or systemic therapy (i.e., other chemotherapy or interleukin-2 (IL-2)-based immunotherapy) (Agarwala, 2010). Unfortunately, response rates are poor with patients having a median overall survival (OS) between 5 to 11 months and a survival rate of 27% for one year. Advanced melanoma patients, as characterized by the American Joint Committee on Cancer stage IV have an overall 5-year mortality rate of 90% (Davis, 2019; Korn, 2008).

Treatment options for metastatic melanoma have improved and currently there are 3 immune approved checkpoint inhibitors (CPIs) available: nivolumab and pembrolizumab (anti-programmed cell death protein 1 [PD-1] antibodies), and ipilimumab (anti-cytotoxic T-lymphocyte-associated protein 4 [CTLA-4] antibody) (Davis, 2019). Antitumor responses in preclinical and clinical trials are observed with antibody blockade of either PD-1 or CTLA-4 (Okazaki, 2007; Peggs, 2008). When PD-1 and CTLA-4 are successfully inhibited in metastatic melanoma, 25%-50% of patients achieve 6 months progression-free survival (PFS) (Byrne, 2017). One-year survival rate of patients with melanoma was 62% when treated with nivolumab (Topalian, 2014). The estimated 5-year OS rate was 34% and the objective response rate (ORR) was 41% with pembrolizumab (KEYNOTE-001) (Hamid, 2019). Ipilimumab has demonstrated a median OS of 11.4 months with a 3-year survival rate estimated to be 22% (Schadendorf, 2015). Combination treatment of ipilimumab and nivolumab results in an ORR of 53% (Wolchok, 2013). An additional treatment option of relatlimab (anti-LAG-3 [lymphocyte antigen-3] antibody) and nivolumab showed an improved mPFS of 10.12 months (95% CI: 6.37, 15.74) as compared with nivolumab monotherapy at 4.63 months (95% CI: 3.38, 5.62) (HR 0.75 [95% CI: 0.62, 0.92]; p=0.0055 with the greatest improvement seen in patients with LAG-3 expression $\geq 1\%$ (Lipson, 2021).

Melanoma has one of the highest mutational loads of all cancers, largely arising from somatic mutations. Of these, approximately 70% have mutations in mitogen activated protein kinase (MAPK) signaling pathways and approximately 50% have activating BRAF mutations – the most common being the V600E mutation (Davis, 2019; Byrne, 2017). In patients with BRAF^{V600E/K} mutant melanoma, treatment with the BRAF inhibitor vemurafenib demonstrated a response rate of approximately 76% when treated with a combination of BRAF and MEK inhibitors, however over 95% will relapse (Schreuer, 2017; Rebecca, 2020). Cancers with high mutational loads like melanoma are associated with better responses to CPIs likely due to their poor capacity in repairing DNA damage (Byrne, 2017).

The safety profile of immune CPIs is well-established. The most common adverse events (AEs) of any grade with PD-1/L1 and CTLA-4 inhibitors were diarrhea, fatigue, pruritus and rash (Arnaud-Coffin, 2019). The most common treatment-related adverse events (TRAEs) in patients with melanoma receiving nivolumab were fatigue (32%), rash (23%), and diarrhea (18%), with 22% of patients experiencing Grade 3 or 4 TRAEs but no drug-related deaths (Topalian, 2014). Of the melanoma patients treated with pembrolizumab, 17% had grade 3 or 4 TRAEs, and only 10% had to discontinue treatment due to TRAEs (Hamid, 2019). Immune-related adverse events (irAEs) are from the excessive activation of the immune system and can lead to serious adverse events (SAEs), interruption or discontinuation of treatment (Bajwa, 2019). Patients with metastatic melanoma administered ipilimumab commonly have irAEs, the most common adverse events (AEs) being diarrhea, hepatotoxicity, hypophysitis, uveitis, pneumonitis, and neurotoxicity (Horvat, 2015). Patients taking the BRAF inhibitor, vemurafenib, most commonly experienced: cutaneous events, arthralgia, and fatigue; 38% of patients had AEs leading to dose interruption or modification (Chapman, 2011). Common irAEs in the combination of relatlimab and nivolumab include hypothyroidism/thyroiditis, rash, diarrhea/colitis, hyperthyroidism, hepatitis, adrenal insufficiency, pneumonitis, hypophysitis, nephritis/renal dysfunction, and hypersensitivity. Grade 3/4 TRAEs occurred in 18.9% of patients on relatlimab and nivolumab as compared with 9.7% of patients on nivolumab (Lipson, 2021).

4.2. Study Rationale

The frontline treatment of metastatic melanoma has evolved over the past decade and now centers around immune CPIs, such as pembrolizumab or nivolumab, which block PD-1, leading to augmentation of anti-tumor immune responses (Robert, 2015). These agents are approved alone or in combination with other therapies. While addition of the immune CPI, ipilimumab, which targets the immune checkpoint CTLA-4, to nivolumab leads to significantly improved PFS over nivolumab alone, the combination has substantially more toxicity and discontinuations due to AEs (Larkin, 2015). As a result, many physicians and patients prefer PD-1/L1 blockade alone (Jenkins, 2021). Attempts to improve ORR and PFS with PD-1/L1 monoclonal antibodies (mAbs) with other agents in BRAF-wild type melanoma have not yet been successful (Jenkins, 2021). Recent review of data from the RELATIVITY-047 study demonstrated improvement in mPFS using the combination of relatlimab with nivolumab over nivolumab monotherapy (Lipson, 2021). In BRAF-mutant melanoma, combined BRAF/MEK inhibitors plus PD-1/L1 mAbs show enhanced ORR and randomized trials to determine effects on OS and PFS are underway (e.g., NCT03455764, NCT03272464).

Taken together, despite the advances of BRAF/MEK, PD-1/L1, PD-1 with LAG-3, and CTLA-4 inhibitors, many patients experience relapse or remain refractory, leaving an unmet clinical need for beneficial long term and curative treatment for metastatic melanoma (Byrne, 2017).

The increased use of CPIs for the treatment of melanoma has changed the treatment paradigm due to the durable clinical benefits noted from this. The concerns have now become related to the majority of patients who either exhibit no response from anti-PD-1/L1 mAbs or those who have a response followed by disease progression (Kluger, 2020). These patients have few treatment options and represent an unmet medical need. Patients who have disease that is considered resistant to anti-PD-1/L1 therapy are broken down into 3 categories:

- Primary resistance

- Secondary or acquired resistance
- Progression after treatment discontinuation

Patients with primary resistance to PD-1/L1 inhibitors are defined by inability of their immune cells to mount an antitumor response as noted by stable disease (SD) lasting for <6 months or no response to therapy. The potential reasons for this include ineffective priming of T cell response, lack of tumor recognition due to defective antigen presentation, inability of T cells to eliminate tumor cells due to bypass pathways, an abundance of immune inhibitory cells like M2 macrophages, or other reasons that have yet to be identified. Patients with primary resistance typically are exposed to immunotherapies between 6 weeks and 6 months. In order to determine whether the patient has primary resistance, a confirmatory scan should be performed at least 4 weeks after the initial diagnosis of disease progression ([Kluger, 2020](#)).

Patients with secondary resistance to immunotherapies had a confirmed objective response or prolonged SD ≥6 months but develop disease progression. The types of resistance may involve adaptation of the tumor cells or due to epigenetic, transcriptomic, and/or proteomic changes to the tumor, alterations in antigen presentation, upregulation of alternative immune checkpoints, or changes in the tumor microenvironment, including numbers of regulatory T cells, myeloid-derived suppressor cells, and M2 macrophages. These are also referred to as acquired resistance to immunotherapies. In order to determine whether the patient has secondary resistance, a confirmatory scan should be performed to demonstrate that there was no presence of tumor flare ([Kluger, 2020](#)).

Disease progression after discontinuation of CPIs is often seen when patients are treated with either adjuvant or neoadjuvant therapy where duration of therapy is limited. Patients may develop a relapse once the therapy has stopped. This may be related to the inability of immunotherapies to eradicate malignant cells due to limited antigen presentation or due to PD-1 receptor decline that occurs over time. Adequate observation of disease progression is that which is seen within 6 to 12 weeks after the last dose of adjuvant therapy ([Kluger, 2020](#)).

The LEAP-004 study evaluated the use of pembrolizumab with the vascular endothelial growth factor receptor (VEGFR) tyrosine kinase inhibitor (TKI) lenvatinib in patients who had progressive disease (PD) while on anti-PD-1 mAb. The ORR in advanced melanoma patients with confirmed progression on CPI therapy was 21.4% (95% CI: 13.9, 30.5) with a DCR of 66.0% (95% CI: 56.0, 75.1). The median PFS was 4.2 months (95% CI: 3.8, 7.1) and the median OS was 14.0 months (95% CI: 10.8, Not reached). The majority of patients (62 out of 103; 60.2%) had primary resistance to anti-PD-1 mAb in the metastatic setting ([Arance, 2021](#)).

Despite the improvement seen in patients with this combination, patients develop rapid disease progression and require improved treatment options in both the primary and acquired resistance groups. The activity of selinexor may allow patients to have reactivation of their tumor to CPI therapy.

